Protocol Study

Comparison of 3 direct laryngoscopes: Inscope DL blade size 3.5 and DL blade 3.5 Sun-Med GreenLine®/D™ to DL blade 3 SunMed GreenLine®/D™ for tracheal intubation in patients undergoing lumbar spine surgery, a prospective randomized study

11/06/2016

NCT02955511

Study Proposal

Comparison of 3 direct laryngoscopes: Inscope DL blade size 3.5 and DL blade 3.5 Sun-Med GreenLine®/D™ to DL blade 3 Sun-Med GreenLine®/D™ for tracheal intubation in patients undergoing lumbar spine surgery, a prospective randomized study

PRINCIPAL INVESTIGATOR

[name]., PhD., Program Director

CO-INVESTIGATORS

[name]
[name]
[name]
[name]
[name]
[name]

STUDY STAFF

INSTITUTION

Department of Anesthesiology
Cedars-Sinai Medical Center in Los Angeles
[name]
[name]

E-mail: [contact]

[contact]

[contact]

STUDY OBJECTIVES

Hypothesis

The use of Macintosh blade sized #3.5 (vs Macintosh size #3) would reduce the time required to achieve successful tracheal intubation and improve the glottic view.

Study objective

The purpose of this research study is to compare 3 different laryngoscope blades (sizes: 3.5, 3.5 and 3) and see if the blades size 3.5 will reduce the time required to achieve successful tracheal intubation and improve the physician's view of the glottis compared to the standard direct laryngoscope using the blade size 3, in patients undergoing lumbar surgery. The Sun-Med GreenLine®/D™ Macintosh Blade laryngoscope (size 3 and size 3.5) are already used at Cedars-Sinai Medical Center, but the Inscope Direct Laryngoscope (size 3.5) will be used at Cedars-Sinai Medical Center for the first time, as part of this research.

Primary end point: time to achieve successful tracheal intubation.

Secondary end points: glottic view at intubation, number of intubation attempts and effectiveness of the integrated suction in the Inscope Direct Laryngoscope.

BACKGROUND AND SIGNIFICANCE

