- (A) Before the case begins, each anesthesiologist will be informed which group the patient has been assigned to. The name of the assigned intubation device will be placed in sealed envelope and given to the participating anesthesiologist after they obtained informed consent and completed the patient's airway evaluation.
- (B) In order to help eliminate bias, the anesthesiologist's experience with each of the intubating devices in 10 or more patients will be verified.

Data of demographic information and physical exam performed (e.g., vital signs and airway evaluation) will be collected.

Il Operative period:

- (A) The randomly selected intubating device (blade) will be prepared and the endotracheal tube will be selected by the attending anesthesiologist.
- (B) The patient will be transported to the operating room and attached to all ASA standard monitors in the usual and customary fashion.
- (C) Standard monitoring devices: an automatic blood pressure cuff, three-lead electrocardiogram, capnograph, pulse oximeter, and an EEG bispectral (BIS) index monitor.
- (D) Midazolam 2mg will be giving as pre-medication.
- (E) The patient will be positioned on the OR table using a donut head pad to create an angle of approximately 30 degrees and bringing the chest up so the sternal notch is at the level of the external auditory meatus.
- (F) The patient will be pre-oxygenated 100% oxygen for 3 to 5 min prior to induction of anesthesia using a facemask to achieve a baseline O2 saturation greater than 98%.
- (G) A standardized induction technique (Standard of care induction) consisting of fentanyl 100 mcg IV, propofol 2 to 2.5 mg/kg IV, lidocaine 1 to 1.5 mg/kg IV, and succinylcholine 1 to 1.5 mg/kg IV. Supplemental bolus doses of propofol will be administered to increase the depth of anesthesia if necessary. If the anesthesiologists consider, additional doses

- of anesthetics will be administered to keep a BIS value < 60. Maintenance of the anesthesia with propofol infusion, cisatracurium, and other medications (and dosages) selected by the attending anesthesiologist.
- (H) The anesthesiologist will determine that the patient is adequately relaxed by verifying the patient has no twitches using a train-of-four nerve stimulator prior to laryngoscopy.
- (I) The investigator will begin timing as the anesthesiologist attending introduces the intubating device into the patient's mouth, obtains glottic view, intubates and End Tidal CO₂ returns.

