- (J) The attending will let the study coordinator know the POGO (Percentage Of Glottic Opening) and the best glottic view grade obtained using the POGO grading system (0% to 100%), and the Cormack Lehane scoring system (1/2/3/4).
- (K) If the intubation attempt is unsuccessful, time will be stopped when the anesthesiologist removes the intubating device from the mouth.
- (L) Rescue with bougie, Mac #4, fiberoptic bronchoscope, LMA, videolaryngoscope or any device necessary used by the attending anesthesiologist will be recorded. Should the need for an adjunct airway device be necessary for ventilation, any device can be used in accordance with the American Society of Anesthesiologist (ASA) difficult airway algorithm in case of a difficult airway.
- (M) If the anesthesiologist uses the suction, its time and frequency will be recorded.
- (N) Vital signs (MAP, heart rate, end-tidal CO2 and SpO2) obtained at standardized intervals before, during and after tracheal intubation will be recorded.

III Post-operative period:

A postoperative follow-up assessment will be performed approximately 4 hours after surgery by a co-investigator blinded to the intubation device to evaluate:

- 1. The presence and severity of sore throat,
- 2. Any changes in voice (e.g., hoarseness),
- 3. Trauma to the lip,
- 4. Trauma to the tongue,
- 5. Trauma to the gum, or
- 6. Trauma to the teeth.

II. Data Analysis:

The total study size is estimated to be 120 patients. A sample size of 40 patients in each group is determined by power analysis based on:

The primary and secondary hypotheses, namely the mean time required to complete the intubation process, for each of 2 DL groups compared with the control (standard DL) group and with each other (i.e., Group 1 vs. Group 2, Group 1 vs. Group 3, Group 2 vs. Group 3). In a single factor ANOVA study, sample sizes of 40, 40, and 40 are obtained from the 3 groups whose means are to be compared. The total sample of 120 subjects achieves 88% power to detect a difference of at least 10 seconds using the Tukey-Kramer (Pairwise) multiple comparison test at a 0.05 significance level. The common standard deviation within a group is assumed to be 8.60.

The following items will be analyzed:

- 1. Demographic information (weight, height, BMI, age, gender)

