- Airway evaluation: Mallampati class, mouth opening, presence or absence of teeth, gaps, thyro-mental distance, neck range of motion (Patients will be asked to move their neck in extension, flexion, rotation, and lateral binding)
- 3. Vital signs (MAP, heart rate, end-tidal CO2 and SpO2) obtained at standardized intervals before, during and after tracheal intubation
- 4. Type and amount of drugs administered during induction
- Assessment of the glottic view using the Cormack Lehane and POGO scoring systems at the time of tracheal intubation
- 6. Times from the passage of the blade between the teeth to obtain glottic view, to placement of the tracheal tube and the appearance of an end-tidal CO2 waveform
- 7. The number of intubation attempt(s) An intubation attempt was defined as the insertion of the laryngoscope blade in to the mouth of the patient, regardless of whether an attempt was made to insert a tracheal tube
- 8. The need to change to a different intubating device, and use of adjuvant airway device (eg, LMA, Bougie, fiberoptic bronchoscope, videolaryngoscope)
- 9. The use of suction and frequency
- 10. The presence and severity of trauma to the lip, tongue, gum, or teeth during intubation
- 11. The presence and severity of sore throat, any changes in voice, trauma to the lip, tongue, gum, or teeth in the recovery area
- 12. Blade Stained with Blood
- 13. Any complications

Definitions:

Intubation attempt: laryngoscope blade is inserted into the study participant. A failure will be recorded if the assigned laryngoscope is removed from the mouth to re-position twice.

Intubation Time: The time starts when the tip of laryngoscope blade passes the upper incisors and the time stops when the endotracheal tube is placed in the trachea, the cuff in inflate, and positive end-tidal CO2 detected.

Time to visualized vocal cords: The time starts when the tip of the video laryngoscope passes the upper incisors and the time stops when the provider has clearly visualized the vocal cords.

Ease of intubation: Immediately after the surgery, the performing anesthesiologist will be asked to judge the ease of intubation with each device on a scale from 1 to 4, where 1 = easy insertion without need of adjustment; 2 = need of one adjustment; 3 = two or more adjustments to obtain optimal visualization of the vocal cords, and 4 = impossible visualization and blind intubation or necessary use of an alternative airway device.

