The provider will clear secretions as necessary to visualize and report the secretions encountered on a scale from 1 to 10, where 1 = no secretions and no visual obstruction 10=severe visual obstruction, unable to clear without removing device.

Postoperative evaluation: sore throat (0 = none and 10 = maximum discomfort), and whether they have postoperative dysphonia. Furthermore, the incidence of postoperative airway complications will be reported.

INCLUSION AND EXCLUSION CRITERIA

It is anticipated that approximately 120 patients age greater than 18 years scheduled to undergo lumbar spine surgery procedures will be enrolled in this study.

A. Inclusion Criteria

Subjects may be included in the study only if they meet all of the following criteria:

- 1) Patients scheduled to undergo lumbar spine surgery procedures under general anesthesia
- 2) Patients with a documented BMI of <35
- 3) Willingness and ability to sign an informed consent document
- 4) 18 80 years of age of either gender
- 5) ASA Class I– III adults

B. Exclusion Criteria

Subjects will be excluded from the study for any of the following reasons:

- 1) Patients who are deemed to be such a significant of an airway risk that they necessitate awake fiberoptic intubation or a difficult tracheal intubation is anticipated
- 2) Patients with history of difficult intubation
- 3) Patients with oxygen saturation less than 95% at room air
- 4) Patients with history facial abnormalities, oral-pharyngeal cancer or reconstructive surgery
- 5) Any pathologies of the mouth, pharynx or larynx, or the access to the airway is restricted
- 6) Patients with Immobilized cervical spine, or history of cervical abnormalities
- 7) Patients with a history of uncontrolled gastroesophageal reflux, hiatus hernia or diabetic gastroparesis
- 8) Any coagulation disorder
- 9) Pregnant patients
- 10) Emergency surgeries
- 11) Any other conditions or use of any medication which may interfere with the conduct of the Study

DATA HANDLING/RESOURCING: Physician Investigators will have access to the patients' medical records as part of this clinical study. All data will be recorded in forms provided by the Investigator(s). Collected data will be coded and used for research purposes only.

SUBJECT RECRUITMENT: Physician Investigators will interview and explain the details of the study to all potential subjects, who will subsequently be asked to sign an informed consent form to participate in this study.

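### Minor, cost-free improvement: record the 1-4 ease-of-intubation score when the tube is confirmed, not after the lumbar operation

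*Protocol*

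**What the plan says.** **Timing and rater.** The Definitions in the protocol and in the SAP carry the same sentence: "Immediately after the surgery, the performing anesthesiologist will be asked to judge the ease of intubation with each device".

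**Scale.** Level 1 is insertion with no adjustment. The middle levels are "2 = need of one adjustment; 3 = two or more adjustments to obtain optimal visualization of the vocal cords". Level 4 is impossible visualization with blind intubation, or the need for another airway device.

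**Knowledge of the device.** Protocol, pre-operative period, item (A): "each anesthesiologist will be informed which group the patient has been assigned to".

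**The operator's other scores.** The Data Analysis list has "Assessment of the glottic view using the Cormack Lehane and POGO scoring systems at the time of tracheal intubation". Operative period, item (J), gives the route: "The attending will let the study coordinator know the POGO", with the Cormack-Lehane grade alongside.

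**Interval.** The population is "Patients scheduled to undergo lumbar spine surgery procedures under general anesthesia". Operation length is not stated.

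**Blinded assessment.** Only the follow-up about 4 hours after surgery is done "by a co-investigator blinded to the intubation device to evaluate". It covers sore throat, voice and trauma, not ease.

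**Status of the score.** Study objectives names intubation time as primary, then "Secondary end points: glottic view at intubation, number of intubation attempts and effectiveness of the integrated suction in the Inscope Direct Laryngoscope". Ease is in neither place, and it is not one of the 13 items listed for analysis in either document.

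**The concern.** The score turns on a count of brief manoeuvres made within one laryngoscopy. Intubation comes before surgery, so the whole lumbar operation lies between the event and the rating. An operator asked at the end has to remember whether there was no adjustment, one, or more, and may be influenced by how the case went afterwards.

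Random recall error blurs a real difference between blades. Recall error that favours one blade can produce a difference that does not exist. A score not taken at the time cannot be recovered later.

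The words "Immediately after the surgery, the performing anesthesiologist will be asked to judge the ease of intubation with each device" raise a smaller matter too. Each patient is randomised to one of three blades, so a rating of each device does not fit a single intubation. It can be read as asking for a comparison across blades, which one patient cannot supply.

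**Working it through.** The plan gives no figure for the ease score, so there is none to reproduce. The check is first textual, then an illustration on assumed inputs.

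**1. Is the adjustment count recorded anywhere at intubation?**

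| Ease level | Depends on | Recorded at the time? |
|---|---|---|
| 1, 2, 3 | Number of adjustments (0, 1, 2 or more) | Not listed |
| 4 | Impossible view with blind intubation, or another device needed | Largely: rescue is recorded (Operative period, item L), as is device change (analysis item 8) |

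Attempts (analysis item 7) do not stand in for adjustments. An attempt is defined by blade insertion, and an adjustment need not involve taking the blade out. Times and glottic view are recorded but do not give the count. Levels 1 to 3 therefore rest on memory.

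**2. Does the earlier moment already exist?** Yes. An investigator is timing the intubation until end-tidal CO2 returns (item I), glottic view is assessed at intubation (analysis item 5), and the attending passes the view scores to the coordinator (item J). The documents give no reason for deferring ease.

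**3. How large could the loss be?** Only the 40 per arm comes from the documents. Everything else here is assumed.

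- Score distributions over levels 1/2/3/4: 40/35/15/10% in one arm and 70/20/7/3% in the other.
- Test: two-sided Mann-Whitney at 0.05. The plan names no test for ease.
- Recall error: a stated share of ratings moves one level up or down at random. A move that would leave the scale has no effect.
- Simulation: 3,000 or 4,000 trials per scenario. At 4,000 trials and power near 70%, the simulation standard error is √(0.70 × 0.30 / 4,000) = 0.7 percentage points.

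| Ratings misrecalled | Power |
|---|---|
| 0% | about 79% |
| 5% | about 78% |
| 10% | about 74% |
| 20% | 68-70% |
| 40% | 55-58% |

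The loss is about 1 point at 5% error (79 − 78), 5 at 10% (79 − 74), 9 to 11 at 20% and 21 to 24 at 40%. If errors at the ends of the scale always move inward instead, power is lower: about 62% at 20% error and 45% at 40%.

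**4. One-directional recall with no true difference.** Suppose ratings in one arm only are recalled one level easier. With 30% of that arm affected, the false-positive rate is about 8% to 15%, depending on the assumed distribution. With 5-10% affected it stays at about 4-6%, close to the nominal 5%.

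**5. Effect of the change on the design.** Moving the rating alters no sample size, alpha or stated power. The plan's power statement concerns intubation time only.

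**The case against.** The case against giving this weight is strong, and most of it stands.

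- **The score is peripheral.** It is neither a named endpoint nor a listed analysis item, and no hypothesis or power statement rests on it. This stands and sets the priority.
- **The timing does not cause the unblinding.** A reader might infer that the late rating is what exposes the score to an unblinded operator. It is not. The operator learns the allocation before the case and would know the blade at whatever moment the rating was made. Any preference for a new device would largely remain after the change. Only the recall and hindsight part is due to timing.
- **Hindsight is partly inferred.** A reader might also infer that the rater has watched the whole case. That is plausible, but the documents do not say that the intubating anesthesiologist stays throughout.
- **The scale is coarse and the operators are experienced.** Recalling one airway on a scale of none, one, or more may be fairly accurate. If error is 5-10%, little is lost. The documents cannot settle the rate, and they give no evidence that recall differs by device.
- **Related facts are recorded.** Rescue, device change, attempts, times and glottic view limit drift, mainly at level 4. They do not separate levels 1 to 3, so this answers the point only in part.
- **The reference to each device may be loose drafting.** Randomisation to one blade makes the sense clear enough. This part is editorial.

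The documents contain no rule that the stated timing breaks. The benchmark is the plan's own handling of glottic view.

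**Conclusion.** The point holds as a free improvement of minor priority. Both documents defer to the end of surgery a score whose levels 1 to 3 depend on a count not listed as recorded, although the same operator's other scores are assessed at intubation. That adds avoidable recall and hindsight error to a score that is already unblinded and would stay so.

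The primary endpoint and the three named secondary endpoints are untouched, so it would be wrong to read this as a threat to the trial's main conclusions. The size of the effect is unknown. Under the assumed distributions, the power loss runs from about 1 point at 5% recall error to 21-24 points at 40%. The documents do not show where in that range the trial would fall. Inflated false positives would require recall that differs by device, for which the documents offer no support.

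**What to change.** In the Definitions of both documents, replace the timing sentence with: *Immediately after end-tidal CO2 confirms tube placement, the performing anesthesiologist reports the ease of intubation with the assigned device (1 to 4) to the study coordinator, together with the POGO score and Cormack-Lehane grade.* The scale anchors stay as they are.

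The cost is one sentence in each document and one line moved on the case report form. It needs no added staff or procedure and makes no change to clinical management, sample size or alpha. It should be in place before data collection. The score should still be reported as an unblinded operator rating.

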## **Data Analysis:**

The total study size is estimated to be 120 patients. A sample size of 40 patients in each group is determined by power analysis based on:

The primary and secondary hypotheses, namely the mean time required to complete the intubation process, for each of 2 DL groups compared with the control (standard DL) group and with each other (i.e., Group 1 vs. Group 2, Group 1 vs. Group 3, Group 2 vs. Group 3). In a single factor ANOVA study, sample sizes of 40, 40, and 40 are obtained from the 3 groups whose means are to be compared. The total sample of 120 subjects achieves 88% power to detect a difference of at least 10 seconds using the Tukey-Kramer (Pairwise) multiple comparison test at a 0.05 significance level. The common standard deviation within a group is assumed to be 8.60.

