The Inscope Direct Laryngoscope has been developed as a Macintosh 3.5 sized blade to meet the size requirements of the majority of patients. This assumption is backed up by a trend among disposable direct laryngoscope manufacturers toward the 3.5 blade size, with at least 5 creating a 3.5 blade, including Teleflex, Sun-Med, Flexicare, Mercury Medical, and Curaplex.

In this study, we will compare the Inscope Direct Laryngoscope (blade size 3.5) with the currently used standard single-use Sun-Med Greenline/D Macintosh laryngoscopes DL-blade mac size and Sun-Med Greenline/D-blade size 3.5

All Direct Laryngoscopes are considered a Class I exempt device by the FDA. Because the risks associated with laryngoscopes are well known and documented, they are considered a non-significant risk device for studies involving humans.

STUDY DESIGN

This randomized, prospective study will analyze the efficacy of three different airway intubating devices. The three different devices are as follows:

- 1. DL-blade mac size 3 (Sun-Med GreenLine®/D™ Macintosh)
- 2. Inscope DL-blade size 3.5
- 3. DL-blade mac size 3.5 (Sun-Med Greenline®/D™ Macintosh)

The Investigator will record the patient's BMI, Mallampatti classification,^{6,7} size of mouth opening, thyro-mental distance, presence or absence of teeth, any unusual physical exam findings, time to successful intubation, number of unsuccessful attempts and the obtained glottic view. The necessity of rescue using a bougie, Mac #4, fiberoptic bronchoscope, LMA or videolaryngoscope. Also the end Tidal CO2 return, as well as the airway grade obtained by the anesthesiologist during intubation using the Cormack-Lehane classification^{8,9} and POGO score ¹⁰ in order to objectively assess and compare the two intubation techniques. Any other unusual events will be documented. All variables for all devices will be compared, evaluated and analyzed.

STUDY METHODS:

| Recruitment and Pre-operative period:

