## The following items will be analyzed:

- 1. Demographic information (weight, height, BMI, age, gender)
- Airway evaluation: Mallampati class, mouth opening, presence or absence of teeth, gaps, thyro-mental distance, neck range of motion (Patients will be asked to move their neck in extension, flexion, rotation, and lateral binding)
- 3. Vital signs (MAP, heart rate, end-tidal CO2 and SpO2) obtained at standardized intervals before, during and after tracheal intubation
- 4. Type and amount of drugs administered during induction
- 5. Assessment of the glottic view using the Cormack Lehane and POGO scoring systems at the time of tracheal intubation
- 6. Times from the passage of the blade between the teeth to obtain glottic view, to placement of the tracheal tube and the appearance of an end-tidal CO2 waveform
- 7. The number of intubation attempt(s) An intubation attempt was defined as the insertion of the laryngoscope blade in to the mouth of the patient, regardless of whether an attempt was made to insert a tracheal tube
- 8. The need to change to a different intubating device, and use of adjuvant airway device (eg, LMA, Bougie, fiberoptic bronchoscope, videolaryngoscope)
- 9. The use of suction and frequency
- 10. The presence and severity of trauma to the lip, tongue, gum, or teeth during intubation
- 11. The presence and severity of sore throat, any changes in voice, trauma to the lip, tongue, gum, or teeth in the recovery area

- 12. Blade Stained with Blood
- 13. Any complications

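### The one-way ANOVA for intubation time is valid but leaves four baseline airway measures out of the model; prespecified adjustment is a cheap improvement whose gain depends on an R² the documents do not give

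*SAP*

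**What the plan says.** Both the SAP (Data Analysis) and the Protocol (Data Analysis) name one model for intubation time, inside the sample-size paragraph: "In a single factor ANOVA study, sample sizes of 40, 40, and 40 are obtained from the 3 groups". Device is the only factor. The three pairs are tested by Tukey-Kramer at 0.05, each 3.5 blade being "compared with the control (standard DL) group and with each other". On variability: "The common standard deviation within a group is assumed to be 8.60". The paragraph claims 88% power for a difference of 10 s.

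The baseline measures appear elsewhere. Protocol, Study Design, has the investigator record BMI, Mallampati class, "size of mouth opening, thyro-mental distance, presence or absence of teeth", and says that every variable will be compared across devices. The SAP list of items to be analyzed has BMI under demographics and then "Airway evaluation: Mallampati class, mouth opening, presence or absence of teeth, gaps, thyro-mental distance, neck range of motion". Neither document makes any of these a covariate or a stratification factor for intubation time.

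On timing, Protocol, Recruitment and Pre-operative period, says the sealed device name is "given to the participating anesthesiologist after they obtained informed consent and completed the patient's airway evaluation". BMI is needed for eligibility ("Patients with a documented BMI of <35"), so it too is known before the device is revealed.

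**The concern.** Measures that describe airway anatomy may explain part of the patient-to-patient variation in intubation time. If they do, a model containing them has a smaller residual variance, and every pairwise device comparison becomes more precise with no extra patients. Because they are measured before the device is revealed, adjusting for them cannot introduce post-allocation bias.

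The width of the simultaneous intervals is at stake, and with it the power for differences smaller than 10 s, for example between the two 3.5 blades. Prespecification matters as well: many baseline variables are recorded, and with no list fixed in advance, any later adjustment would be a post hoc choice among them.

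**Working it through.** **Inputs from the documents.** 40 patients per arm in three arms; SD 8.60 (no unit printed, taken as seconds); target difference 10 s; Tukey-Kramer at familywise 0.05.

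**Assumptions.** R², the share of variance in intubation time explained by the four covariates, is in neither document, so 0 to 30% is shown. The 6 s difference is illustrative. Every patient is taken to contribute a time.

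**Step 1: the plan's own figure.** Error df = 120 − 3 = 117.
- Critical value: q(0.95; 3, 117)/√2 = 2.3739.
- SE of a pairwise difference: 8.60 × √(2/40) = 1.923 s.
- Noncentrality at 10 s: 10/1.923 = 5.20, giving per-pair power of 99.7% by the noncentral t.

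The stated 88% is not reproduced. Per-pair power of 88% would need, for instance, an SD of about 12.6 with the other inputs unchanged.

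**Step 2: unadjusted precision.** Half-width = 2.3739 × 1.923 = 4.57 s. Power at 6 s is 77.1%; 80% power is reached at 6.19 s.

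**Step 3: adjusted precision.** Four covariates, with Mallampati class as a one-df score, leave 113 error df.
- Critical value: q(0.95; 3, 113)/√2 = 2.3750.
- Expected variance inflation from chance imbalance: 1 + 4/(117 − 4 − 1) = 1.0357.
- Half-width: 2.3750 × 8.60 × √[(1 − R²) × 1.0357 × 2/40].
- Change in effective sample size: (4.565/half-width)² − 1.

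| Assumed R² | Half-width (s) | Effective sample size | Power at 6 s | Difference with 80% power (s) |
|---|---|---|---|---|
| unadjusted | 4.57 | reference | 77.1% | 6.19 |
| 0% | 4.65 | −3.5% | 75.4% | 6.31 |
| 5% | 4.53 | +1.5% | 77.8% | 6.15 |
| 10% | 4.41 | +7% | 80.3% | 5.98 |
| 20% | 4.16 | +21% | 85.2% | 5.64 |
| 30% | 3.89 | +38% | 90.0% | 5.28 |

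Power at 10 s stays at 99.7% or above throughout.

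**Step 4: break-even.** R² = 1 − (2.3739/2.3750)²/1.0357 = 3.5%. Below this, adjustment loses precision.

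**Step 5: simulation check.** 12,000 trials per R² value used three normal covariates and a four-level Mallampati score with assumed frequencies of 40/40/15/5%. Mean half-widths were 4.64, 4.52, 4.40, 4.15 and 3.88 s. Familywise error was 5.0 to 5.5% adjusted and 4.7 to 5.3% unadjusted (simulation SE 0.2 points).

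**Step 6: sensitivity to the SD.** If the SD were 12.6 (an assumption chosen because it gives about 88%), unadjusted power at 10 s is 87.8%. Adjusted power at the same five R² values is 86.5, 88.4, 90.2, 93.5 and 96.2%.

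**The case against.** The strongest reply is that nothing is wrong with the plan. The one-way ANOVA is valid, and the only difference the documents name is 10 s, where power on the stated inputs is 99.7% and cannot usefully rise. The gain is shown at 6 s, a value the documents do not use. Even its direction is uncertain: below an R² of 3.5% adjustment costs precision, and at 5% the half-width shrinks by only about 0.035 s. Entry is limited to BMI below 35, and patients who "necessitate awake fiberoptic intubation or a difficult tracheal intubation is anticipated" are excluded, as are those with a history of difficult intubation. That narrows the range of these covariates and makes a low R² plausible. The 20% and 30% rows have no support in the documents.

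All of this stands as a limit on the size of the benefit. It does not show the change to be wrong or costly: the loss is bounded at about 3.5% of effective sample size, and the data are already being collected.

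A reader might also infer that the baseline measures are ignored altogether. The documents do not support that: the measures are listed for analysis and for comparison across devices. What is absent is a role in the intubation-time model.

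**Conclusion.** The point holds as an optional, low-cost improvement. Adjustment would change the Tukey half-width from 4.57 s to between 4.65 s (R² 0%) and 3.89 s (R² 30%), with little gain below an R² of about 5 to 10%. The omission is certain on the text available; a net gain is not, because R² is unknown.

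Two stronger readings should be resisted. One is that the planned comparison is biased or invalid; randomization protects it without any covariate. The other is that the trial needs adjustment to reach its 10 s target; on the stated inputs it does not.

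The absolute figures rest on SD 8.60, which does not reproduce the 88% stated in the same paragraph. That conflict needs its own resolution. If the SD were nearer 12.6, adjustment could matter modestly for the 10 s target itself. The figures also assume that every patient has a time; what a failed or rescued intubation contributes must be settled separately, whichever model is used.

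**What to change.** Prespecify in the SAP, before any outcome data are seen, one primary model for intubation time: device + BMI + Mallampati class (as a score) + mouth opening + thyro-mental distance. Take Tukey-adjusted pairwise contrasts from it and report the one-way ANOVA result alongside. Replace a missing covariate value with that covariate's overall mean.

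Keep the list to these four. A fifth one-df term would raise the expected inflation from 1.0357 to 1 + 5/(117 − 5 − 1) = 1.045, and the documents give no sign that it would repay this.

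The cost is SAP wording only, with no new data and no extra patients. Error degrees of freedom fall from 117 to 113. If the covariates explain nothing, about 3.5% of effective sample size is lost.
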